High indoor allergen and pollutant levels have repeatedly been linked to asthma morbidity, especially among urban children, who have among the highest asthma morbidity in the US. ⁽¹⁻⁵⁾ However, environmental intervention trials for asthma have typically compared an environmental control strategy (ECS) to no intervention, a design that does not reflect the recommended approach to asthma management, which includes ECSs *in conjunction with* titration of controller medication. ⁽⁶⁾ As a result, it remains unknown whether the addition of an ECS to controller medication titration results in improved asthma control, and therefore a reduced controller medication requirement. Another unanswered question is whether the addition of an ECS to controller medication titration results in greater reduction of allergic inflammation than medication titration alone. ECSs may have a greater effect on allergic inflammation than controller medications because ECSs target the most upstream point of the asthma inflammatory pathway by reducing pro-inflammatory environmental exposures, while controller medications target a downstream point of this pathway. ⁽⁷⁻⁹⁾ Surprisingly, it is also unknown whether the improvement in asthma in ECS trials is mediated by reductions in allergen levels and/or reduction in pollutant levels. Understanding the factors that mediate the effects of an ECS on asthma is important for refuting, or supporting, a causal role for indoor allergens and/or pollutants in asthma morbidity, and also for optimizing the design of ECSs to target the most influential factors. We therefore hypothesize that the addition of an individually-tailored, multi-faceted ECS to guidelines-based controller medication titration will result in less controller medication requirement and allergic inflammation than controller medication titration alone among urban asthmatic children. We will test this hypothesis and identify the factors that mediate the clinical effects of the ECS with a parallel-arm, randomized controlled trial of ECS plus controller medication titration vs. controller medication titration alone. Our aims are: **(1)** To determine the effect of the addition of ECS to controller medication titration on controller medication requirements and allergic inflammatory biomarkers, and **(2)** To determine whether reductions in particulate matter (PM) and/or indoor allergens mediate the effects of an ECS on asthma. This proposed trial will answer a pivotal question because if ECSs do not provide additional benefit in the context of treatment with controller medication, the role of ECS in asthma management should be downgraded. On the other hand, if ECSs do indeed reduce controller medication requirements, greater emphasis should be placed on the importance of ECSs in asthma management, studies should be conducted to identify best ECS practices, and policies should be changed to require third party payers to cover ECS costs.

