
2. Objectives

We hypothesize that the addition of an individually-tailored, multi-faceted environmental control strategy (ECS) to guidelines-based controller medication titration will result in less controller medication requirement and allergic inflammation than controller medication titration alone among urban asthmatic children. We will test this hypothesis and identify the factors that mediate the clinical effects of the ECS with a parallel-arm, randomized controlled trial of ECS plus controller medication titration vs. controller medication titration alone. The aims are:

- (1) To determine the effect of the addition of ECS to controller medication titration on controller medication requirements and allergic inflammatory biomarkers.
 - a) To compare the effect of the active intervention (“ECS+Medication Group”) to control (“Medication Group”) on controller medication requirement (“treatment step”) and inhaled corticosteroid dose.
 - b) To compare the effect of the active intervention to control on F_ENO, serum allergen-specific IgE levels.
- (2) To determine whether reductions in particulate matter (PM) and/or indoor allergens mediate the effects of an ECS on asthma.
 - a) To measure the change in fine and coarse particulate matter (PM_{2.5} and PM_{2.5-10}, respectively) and indoor allergen concentrations (cat, dog, mouse, cockroach, and dust mite) among study participants.
 - b) To estimate the causal effects of PM and allergen exposure reduction on controller medication requirements and allergic inflammatory outcomes, using a novel statistical approach, principal stratification analysis.
- (3) To evaluate whether a child’s personal bacterial exposures, particularly those of animal origin, contribute to asthma morbidity.
 - a) To compare bacterial community profiles and *S. aureus* genotypes in children versus pet and pest animals (dog, cat, mouse, cockroach others) in the home.
 - b) To examine associations between the child’s bacterial communities and asthma morbidity.
 - c) To determine relationships between the child’s *S. aureus* colonization and asthma morbidity.

3. Background

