Randomization: Participants will be randomized within 6 weeks (+/- 2 wks) of the screening clinic visit in a 1:1 ratio using a statistical software package to generate random numbers. The randomization scheme will be developed by the Data Management and Analysis Core (DMAC). Participants will be randomized in random block sizes of 4 to 8. The randomization scheme will be embedded into the recruitment/tracking database so that once a participant meets all eligibility criteria the site study coordinator can activate randomization through a secure user interface. The DMAC database programmer will have access to the computer code for the randomization scheme. Participants randomized to the ECS+Medication Group will be scheduled for an intervention prior to their next clinic visit.

ECS Intervention

Skin test data, home inspection data, and environmental history will be used to tailor an ECS to participants randomized to the ECS+Medication Group. Randomization will occur at CV1 and all of the information needed to assign ECS modules will have been collected before randomization. The 5 modules are listed below along with the qualifying criteria to receive the module and a summary of the components of each module (Table 5).

	Qualifying criteria	Components of Module
Rodent module	Positive skin test or IgE* to mouse or rat plus any evidence of infestation on home inspection OR parent report of evidence of infestation in the past month	Professional IPM Targeted cleaning IPM education Allergen-proof mattress and pillow encasements
Cockroach module	Positive skin test or IgE* to cockroach plus any evidence of infestation on home inspection OR parent report of evidence of infestation in the past month	Professional IPM Targeted cleaning IPM education Allergen-proof mattress and pillow encasements
Furry pet module	Positive skin test or IgE* to cat or dog	Education Allergen-proof mattress and pillow encasements Targeted cleaning
Dust mite module	Positive skin test or IgE* to dust mite	Education Allergen-proof mattress and pillow encasements Targeted cleaning
SHS module	Smoker in the home	Education
Air purifiers/Clean Bedding	None – everyone assigned to the ECS+medication arm will receive air purifiers and child’s bedding will be replaced with study bedding for study duration.	Deployment of 2 portable air purifiers, one in the child’s bedroom and one in the TV/living room. Child’s bedding will be replaced with study bedding for study duration.

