Potential confounders will be explored by examining any differences between the intervention and control groups and also assessing the association between the potential confounders at baseline and at the final study visit. In addition, potential confounders will be included in the models to determine the impact the variables have on the relationship between group assignment and the outcome. Some specific confounders that will be carefully examined include baseline allergen and pollutant levels, treatment step at baseline, and season. Potential effect modifiers, such as baseline pollutant and allergen levels, baseline asthma severity, baseline asthma control, baseline lung function, and number of positive skin tests, will also be examined by stratifying analyses and creating an interaction term to include in the final models. Analyses will be stratified by these potential response predictors and interaction terms will be included in models to determine if any of these factors predict responsiveness to the intervention.

To measure the change in home airborne particulate matter (PM_{2.5} and PM_{2.5-10}) and indoor allergen concentrations (cat, dog, mouse, cockroach, and dust mite) among study participants. Distributional properties of baseline levels of pollutants (PM_{2.5} and PM_{2.5-10}) and allergens will be assessed using histograms and boxplots and any necessary transformations to these variables will be conducted to obtain approximately Normal distributions. We will subtract baseline levels of these exposures from levels recorded 6 months post-randomization to assess the within-person change in exposure over time. Differences over time in the intervention group will be compared to those in the control group via standard *t*-tests using a significance cutoff of 0.05. Assessment of significance adjusting for multiple comparisons will be done using the method of Benjamini and Hochberg.

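### Aim 2 asks about mediation, but principal stratification gives the ECS effect by exposure-response group; the Aim 2b claim should be limited to that, with PM and allergens handled jointly

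*Combined protocol and SAP*

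**What the plan says.** Section 2 (Objectives) words Aim 2 as "To determine whether reductions in particulate matter (PM) and/or indoor allergens mediate the effects of an ECS on asthma". Aim 2b gives the target, "To estimate the causal effects of PM and allergen exposure reduction on controller medication requirements and allergic inflammatory outcomes", and the method, "using a novel statistical approach, principal stratification analysis". The opening summary calls knowledge of the mediating factors "important for refuting, or supporting, a causal role for indoor allergens and/or pollutants in asthma morbidity", and also useful for deciding what future strategies should target.

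In section 6.c (Analysis Plan), the paragraph on PM and allergens covers transformation, change from baseline ("We will subtract baseline levels of these exposures from levels recorded 6 months post-randomization"), t-tests between arms and a Benjamini-Hochberg adjustment. Baseline exposure levels also appear there as possible confounders and effect modifiers. No analysis links the change in an exposure to an outcome. Strata, cut-offs for continuous exposures, identifying assumptions and the handling of several exposures together are not given.

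On the intervention, Table 5 says "everyone assigned to the ECS+medication arm will receive air purifiers", together with study bedding. Encasements, targeted cleaning, professional pest management and smoke education are added where the child or home qualifies. The Background section on air purifiers says filtration lowers both PM and furry-animal allergens.

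**The concern.** Principal stratification sorts children by how their exposure would behave under each arm, then compares the arms within each group. Each group's result is the whole ECS effect in that group, by every route. It does not separate the part that passes through PM from the part that passes through allergens, bedding or cleaning.

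The aim asks for that separation. Reported under the present wording, a larger ECS effect in homes where PM would fall would be read as PM mediating the benefit. It could equally mean that those homes also had larger falls in allergens, or made more use of the whole package. At stake is the interpretation of Aim 2, which the opening summary presents as a guide to what future strategies should target.

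**Working it through.** **The plan's own figure.** No figure is given for Aim 2. The scale comes from Table 6: 1 step, SD 2.0, two-sided alpha 0.05 (sidedness assumed), 1:1 allocation. Power = Φ(δ / (σ√(2/n)) − 1.96).
- n = 100 per arm: 1/(2 × 0.1414) − 1.96 = 1.58, power 0.942 (stated 0.94).
- n = 87.5 per arm: 1/(2 × 0.1512) − 1.96 = 1.35, power 0.911 (stated 0.90).

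These reproduce to within about one point and are not in dispute.

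**What a stratum effect contains.** For stratum s, τ(s) = E[Y(ECS) − Y(control) | s] = part through the named exposure + part through all other routes. It is the effect of exposure reduction only if the second part is zero. Table 5 and the Background give reasons to expect otherwise: one universal component moves two candidate mediators, and other components act alongside it.

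**Illustration A: shared engagement (all values assumed).** Household engagement E ~ Beta(2,2). The ECS effect is −2E steps, mean −2 × 0.5 = −1. PM has no effect on step. PM falls with probability 1/(1 + exp(−a(E − 0.5))), so half of homes respond. The stratum effect is −2 × mean E in that stratum.

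| Link a | PM would fall | PM would not fall | False contrast |
|---|---|---|---|
| 6 | −1.23 | −0.77 | 0.46 |
| 3 | −1.14 | −0.86 | 0.28 |
| 0 | −1.00 | −1.00 | 0 |

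**Illustration B: correlated responses (all values assumed).** 60% of children respond on PM and 60% on allergen, from a bivariate normal with correlation ρ. Only allergen responders benefit, by 1/0.6 = 1.67 steps, so the mean is again −1. The stratum effect is −1.67 × P(allergen responder | PM stratum). At ρ = 0.5 the share responding on both is 0.44. Among PM responders, 0.44/0.60 = 0.73 gives −1.22. Among non-responders, 0.16/0.40 = 0.40 gives −0.67.

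| ρ | PM responders | PM non-responders | False contrast |
|---|---|---|---|
| 0 | −1.00 | −1.00 | 0 |
| 0.3 | −1.13 | −0.81 | 0.32 |
| 0.5 | −1.22 | −0.67 | 0.55 |
| 0.7 | −1.33 | −0.51 | 0.82 |

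The true PM-mediated effect is zero in every row of both tables.

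**Joint strata (engagement model, a = 6 for PM and allergen, PM inert).**
- Whole effect through allergen (−2 steps when it falls): the ECS effect is −2.00 or 0.00 according to allergen and the same whether or not PM falls. The false contrast disappears.
- Half through allergen (−1 step when it falls) and half through other components (−E): −1.68 against −1.50 where allergen falls, and −0.50 against −0.32 where it does not. A false PM contrast of 0.18 step remains.

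**Precision of joint strata.** With the ρ = 0.5 shares and 175 children, the PM-only and allergen-only cells hold 0.16 × 175 = 28 each, about 14 per arm. With SD 2, the standard error is 2 × √(2/14) = 0.76, so the 95% interval is about ±1.5 steps, even if membership were known. Aim 2a lists two PM fractions and five allergens; a yes/no response on each gives 2^7 = 128 cells, so a smaller joint definition has to be chosen in advance.

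**The case against.** The strongest reply is that the false contrast comes from taking one exposure at a time, not from principal stratification. A mediation model with PM alone would mislead in the same way, and nothing in the documents says strata would be formed one exposure at a time. This stands in part. Joint strata remove the contrast when allergen carries the whole effect, but 0.18 step remains when half runs through other components.

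Second, the correlation is assumed. Staff install encasements, pest management is professional and bedding is supplied, so these depend less on the family. Allergen modules depend on sensitisation (and infestation, for pests) while purifiers go to everyone, which loosens the link. This stands. In the other direction, the shared purifier makes some correlation plausible.

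Third, the method is informative. Benefit in homes whose PM would not fall shows that the ECS can work without that reduction, which bears on Aim 2. This also stands.

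Fourth, regression mediation is not a safe replacement. It needs no unmeasured exposure-outcome confounding, and engagement is measured only partly: purifier use is logged in a 10% sample. That argues for a supplementary role.

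A reader might also infer that the opening summary fixes a decision for each exposure. It does not: it gives a reason for studying mediators. Its explicit policy consequences concern the ECS effect as a whole.

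**Conclusion.** The mismatch holds in a limited form. Whatever the correlation, a stratum effect is the total effect of assignment in a latent group, so it cannot be reported as mediation or as the effect of exposure reduction unless the ECS acts only through that exposure. The plan neither states nor supports that condition.

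The size is illustrative: a false contrast of about 0.3 to 0.5 step against an assumed 1-step effect, zero with no correlation, and larger (0.8) at the strongest correlation tried. It rests on correlated responses and strata formed on a single exposure, and the documents settle neither.

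It would be tempting to conclude that naming principal stratification means the trial will credit an exposure that does nothing, or that the method is useless here. The documents support neither: joint strata can avoid much of the problem, and effects in non-responders are informative. The primary intent-to-treat comparison and its power are unaffected.

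**What to change.** 1. In Aim 2b and section 6.c, state that the principal stratification result will be reported as the ECS effect in children whose exposure would or would not fall, and not as mediation or as the causal effect of exposure reduction.
2. In section 6.c, define PM and allergen responses jointly. Give the strata, the cut-offs for continuous exposures and the identifying assumptions.
3. If a mediation claim is still wanted, add a supplementary model with changes in PM2.5, PM2.5-10 and allergens entered together. Adjust for baseline exposures, baseline treatment step and season. Add a sensitivity analysis for unmeasured exposure-outcome confounding, naming household engagement.

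No new data are needed, since exposures are already measured at baseline, 3 and 6 months. The cost is analyst time, a more modest Aim 2 claim and wide intervals at about 175 children. The supplementary model exchanges one strong assumption for another, so its result should be presented with that stated.

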Household Members with Asthma: The parent/guardian will be asked about other members of the household who have asthma. These household members will be identified by number only. Age, sex, and information about asthma related health care utilization will be collected from the participant's guardian about other household members who have asthma. If there are other children with asthma, not including the study participant (index child), we will ask the child, 5-17 years of age, and his/her parent/guardian to participate in a sub study. We will ask to draw one tube of blood for specific IgE to cat, dog, mouse, rat, German cockroach, and D. farinae and ask that the Asthma Control Test questionnaire be completed by the child around the time of randomization and the end of the study. This will require a separate consent form. If there is more than one child 5-17 years of age in the household with the index child, the child who will be asked to participate in the study will be chosen based on convenience. The purpose of this sub study is to generate preliminary data to understand how many other household members have asthma and whether the intervention affects asthma control of other children with asthma in the household.

URI Assessment: The parent/guardian and/or adolescent child will be asked questions about recent respiratory illnesses (colds) and a nasal mucus sample will be collected. The child will use a nasal saline spray in each nostril and blow his/her nose into a plastic baggie for the collection of a nasal sample. This will be collected at CV1-4.

Run-in Period and Follow-up Clinic Visits: There will be an approximate 4 week run-in period following the screening visit to stabilize the participant's asthma. Participants will return for CV1 for randomization if they meet adherence eligibility requirements. Once randomized, participants will be prescribed a steroid burst to have at home in the event of an exacerbation. They will then have follow-up CVs every two months with clinical assessment of their asthma, collection of outcome data, and application of the treatment algorithm as described above (Table 2).

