Participants will be enrolled for approximately 7 months. There will be five clinic visits and three home visits over this time period for clinical and home assessments, respectively. There will be up to four environmental intervention visits for participants randomized to the environmental control plus controller medication group. Participants randomized to the controller medication group have the option of having one home visit after completing the study at which they will receive home intervention services that the environmental control plus controller medication group received with the exception of bedding being replaced.

c. Blinding, including justification for blinding or not blinding the trial, if applicable.

Participants will not be blinded because it is not practical and impossible to create a sham environmental intervention without exorbitant costs. The study physicians applying the treatment algorithm, which drives the primary outcome, will be blinded to the extent possible. For example, study staff will be trained not to divulge the participants' randomization group to the physician during the clinic visit.

d. Justification of why participants will not receive routine care or will have current therapy stopped. Participants will be asked to stop anti-histamines for approximately 5 days prior to skin testing at the screening visit since anti-histamines interfere with the skin test results. Otherwise, all participants will receive national guidelines-based titration of controller medication and education about asthma management.

e. Justification for inclusion of a placebo or non-treatment group.

Although there are two groups being compared in this trial, there is no group that is not receiving guidelines-based asthma treatment.

f. Definition of treatment failure or participant removal criteria.

A study participant will be discontinued from further study intervention if any clinical adverse event, other medical condition or situation occurs such that continued participation in the study would not be in the best interest of the participant.

This includes: (1) an asthma hospitalization that results in intubation and (2) a second asthma hospitalization during the course of the study.

g. Description of what happens to participants receiving therapy when study ends or if a participant's participation in the study ends prematurely.

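### The household sub study picks the other child by convenience and does not secure choice, consent or the first Asthma Control Test before allocation is known

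*Combined protocol and SAP*

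**What the plan says.** The sub study is described in the Study Procedures section, part a, under Household Members with Asthma. It enrols another child aged 5-17 with asthma who lives with the index participant. It has two stated purposes: to count other household members with asthma, and to see "whether the intervention affects asthma control of other children with asthma in the household". The second is a comparison between arms. The section limits its ambition: "The purpose of this sub study is to generate preliminary data".

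Three features matter here.

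- **Choice of child.** If more than one child qualifies, "the child who will be asked to participate in the study will be chosen based on convenience".
- **Timing of the measurements.** The Asthma Control Test is to "be completed by the child around the time of randomization and the end of the study". No window is given, and the first test is not required to come before allocation.
- **Consent.** "This will require a separate consent form". No time is given for it.

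Part c of the same section, on blinding, says: "Participants will not be blinded because it is not practical". Only the study physicians are shielded from the arm, as far as possible. The means is that "study staff will be trained not to divulge" the arm to them, so other staff can know it. The index child is randomised at CV1, when the coordinator activates allocation through the database. The visit schedule has no row for the sub study, and Section 6 (Study Statistics) has no analysis for it.

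**The concern.** A between-arm comparison of household children is protected by randomisation only if the arm cannot influence who is enrolled or what the first score is. Under the present text it could, in three ways.

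1. **Which child.** In a home with two or more eligible other children, a family or staff member who knows the arm may offer a different child in one arm than in the other. There is a plausible motive. One air purifier, the bedding and the encasements are directed at the index child's bedroom, so a child who shares that room may be thought to benefit more.
2. **Whether any child.** Contact after CV1 differs by arm. ECS homes receive up to four intervention visits, while Medication homes are offered theirs only after the study ends. If recruitment to the sub study runs past CV1, ECS homes give more occasions to ask and obtain consent. This applies even where only one other child qualifies.
3. **The first score.** It is a questionnaire completed by the child. If it follows allocation, expectation can colour it. If it follows the first intervention visit, it is no longer a baseline.

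At stake is the sub study's answer on household benefit. Selection of this kind is hard to repair afterwards, because the plan does not collect test scores on the children who were not chosen.

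**Working it through.** **No stated figure to reproduce.** The sub study has no stated sample size, power or alpha. The main trial's power (0.94 for one treatment step, SD 2.0, n=200) recomputes to 0.942 by the normal approximation with two-sided alpha 0.05, but it does not enter this point.

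**Order of events.**

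| Step | What the text fixes | Before allocation? |
|---|---|---|
| Randomisation of index child | CV1 | reference point |
| Choice of household child | by convenience, no date | not secured |
| Consent of household child | separate form, no date | not secured |
| First Asthma Control Test | near randomisation, no window | not secured |
| First ECS intervention visit | between CV1 and CV2 | after |

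Nothing elsewhere in the document supplies the missing order or a choice rule that cannot depend on arm.

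**Illustrative size of the first route (which child).** Every input below is an assumption; the documents give none of them.

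- q: share of sub-study homes with two eligible other children.
- D = pE - pC: difference between arms in the probability of choosing the child with the worse asthma.
- rho: correlation of scores between two children in one home.

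For two children with standardised normal scores, the better and the worse lie on average sqrt((1 - rho)/pi) above and below the mean. An arm that picks the worse child with probability p therefore has mean (1 - 2p) x sqrt((1 - rho)/pi) in those homes. The absolute difference between arms, over all sub-study homes, is

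imbalance = q x 2 x D x sqrt((1 - rho)/pi).

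With rho = 0.3, sqrt(0.7/3.1416) = 0.472. In SD units of score level:

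| q | D = 0.2 | D = 0.5 |
|---|---|---|
| 0.1 | 0.1 x 0.4 x 0.472 = 0.019 | 0.1 x 1.0 x 0.472 = 0.047 |
| 0.3 | 0.3 x 0.4 x 0.472 = 0.057 | 0.3 x 1.0 x 0.472 = 0.142 |
| 0.5 | 0.5 x 0.4 x 0.472 = 0.094 | 0.5 x 1.0 x 0.472 = 0.236 |

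The range is about 0.02 to 0.24 SD. D = 0.5 already means, for example, that one arm always takes the better-controlled child while the other picks at random, so the right-hand column is pessimistic. If the child is fixed by a rule that cannot depend on arm, D = 0 and the expected imbalance from choice of child is 0.

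The second and third routes (whether any child is enrolled, and a coloured first score) are not in this calculation. The documents give nothing from which to size them.

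**The case against.** The strongest reply is that the text does not say the child is chosen near randomisation. The words "around the time of randomization and the end of the study" govern the questionnaire, and arguably the blood draw, but not the choice or the consent. The paragraph stands among the procedures that begin with the screening visit and before the description of the run-in, so choice before allocation is a natural reading. If that is what happens, the choice cannot depend on arm. This stands, and it limits the claim. A reader might infer that the child is picked once the arm is known, or that the arms do differ. The documents support only that the order is left open. Placement does not close it, since other procedures in the same run take place at CV1-4.

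A reader might also reach for a larger figure. If one arm always takes the better-controlled of two unrelated children and the other picks at random, the shift is 1/sqrt(pi) = 0.56 SD in affected homes, or 0.11-0.23 SD if 20-40% of homes are affected. That rests on zero correlation between children who share a home, on extreme selection, and on a share the documents do not give. An affected home needs the index child plus at least two other asthmatic children of eligible age. With rho = 0.3 the same scenario gives 0.2 x 0.472 = 0.09 to 0.4 x 0.472 = 0.19 SD.

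Two further points stand in part. The test is taken twice, and Section 6 compares changes from baseline for the main outcome, with a similar approach for other clinical outcomes. The same approach here would remove some of a difference in level. A first test taken just after allocation can also still precede the first intervention visit, which leaves expectation rather than treatment effect. Neither point helps if the first score itself depends on the arm.

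Finally, the sub study is preliminary. It is not among the aims or the primary and secondary outcomes. That bears on severity, not on whether to make the change.

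**Conclusion.** The point holds as a gap in protection, not as a demonstrated bias. The plan states a convenience rule, leaves the choice and consent undated, places the first test only near randomisation, and poses a between-arm question in a trial where families know their arm. Selection and the first score can therefore depend on arm.

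The size cannot be derived from the documents. The 0.02 to 0.24 SD range is an illustration in score level. It rests on rho = 0.3, on 10-50% of sub-study homes having two eligible other children, and on a 0.2-0.5 difference in selection probability. Baseline adjustment could remove part of it.

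Severity is low. A reader should not carry this over to the main trial: the index children, the primary outcome and its power are unaffected.

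**What to change.** In the Household Members with Asthma paragraph:

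1. Replace convenience with a fixed rule that cannot depend on arm, for example the child whose birthday comes next after the screening visit among those aged 5-17 with asthma. Record the choice.
2. Require consent and the first Asthma Control Test to be complete before randomisation is activated at CV1. HV-1 falls before CV1, and the database activation step is a natural checkpoint.
3. State that the final score will be compared between arms with adjustment for the first score, and report by arm the numbers of household children eligible, asked and consenting.

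The text change is a few sentences. The practical cost is some loss of convenience, since the child named by the rule may be harder to reach and no visit is scheduled for household children. A few will also be enrolled or tested although the index child is then not randomised, for instance because adherence at CV1 is below 25%. The change does not deal with reporting bias in the final test, which is still answered with the arm known.
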